8.2.4 Choice of Route and Rate of Administration

In the double-blind phase of this study, the subject or their female partner will typically apply one of the three MED2005 gels (0.6 mg GTN, 1.2 mg GTN or 1.8 mg GTN) or the placebo vehicle gel to the glans penis. In the open-label extension phase, all subjects will receive treatment with the 0.6% MED2005 gel to deliver a dose of 1.8 mg GTN.

The IMP will be self- or partner-applied at home. This is the intended method of administration after licensing. Subjects or their partners will be required to apply a single dose (approximately 300 mg) of gel to the glans of the penis and rub for at least 15 seconds (to ensure thorough distribution of the gel and promote penetration of the active substance) immediately prior to sexual intercourse. Subjects will be asked to leave a washout period of at least 12 hours before the next attempt at sexual intercourse using the IMP.

8.2.5 Monitoring and Communication of AEs

AEs will be monitored throughout the duration of the study from signing of the Informed Consent Form (ICF) at screening (Visit 1) until the final study visit. AEs of any untoward signs and symptoms for both the subject and his female partner will be documented in paper diaries to be completed at home by the subjects and their partners as they experience them (i.e. in real time) during each 4-week period in the double-blind phase and each 3-month period in the open-label extension phase and reviewed regularly by the Principal Investigator (PI) or his/her delegate (potential partner AEs will be captured at site visits or by telephone). If any information relating to the study product becomes available after the submission of a final protocol to the Competent Authority which may impact on the conduct of the study, including but not limited to the risk and benefit evaluations underpinning approvals and subject consent, FMD shall notify the study site in writing as soon as practically possible and the parties will agree, in writing, what steps need to be taken, if any.

8.2.6 Study Principal Investigator, Site Facilities and Personnel

This multi-centre study will be conducted at approximately 50 investigational sites in countries including Poland, Hungary, Czech republic, Slovakia, Georgia, Russia, Ukraine, Bulgaria and Latvia. At all sites, the study will be conducted by an experienced PI and well-trained medical, clinical and technical staff with experience in the conduct of clinical studies. The study is designed to closely monitor, treat and communicate potential expected adverse reactions (based on the known mode of action of the IMP) as well as potential unexpected AEs.

8.3 Stopping Criteria

The study will be discontinued if any unacceptable safety findings are identified. This decision will be made jointly by the Chief Investigator (CI) (or deputy) and the Sponsor. A written document signed by the CI (or deputy) and Sponsor will be produced ratifying the decision.

Please see [Section 9.6](#) for possible reasons for discontinuation of an individual subject

The PI and the Sponsor will have joint judgment of an unacceptable tolerability profile (stopping criteria) based on the frequency and intensity of observed AEs (including SAEs and treatment-related AEs).

Any subject suffering from a clinically relevant AE will be monitored closely and provided with the appropriate medical care and follow-up.

9. SELECTION AND WITHDRAWAL OF SUBJECTS

9.1 Number and Source of Subjects to be Studied

It is planned to randomise and treat 1000 male subjects clinically diagnosed with ED, along with their female partners, in the double-blind phase of the study. Additional subjects may be randomised if there are a substantial number of dropouts to ensure that sufficient data are available for analysis; this would be detailed in a protocol amendment. Subjects will be identified and recruited through volunteer databases, site/clinician recruitment and/or advertisements as necessary.

For the open-label extension phase, it is planned to include a total of 450 male subjects and their female partners.

9.2 Inclusion Criteria

All subjects must meet all of the following inclusion criteria to be eligible for the study (following screening [Visit 1], an eligibility check will be carried out on Day 1 of the treatment period [Visit 2]):

1. Subject is a male aged between 18 and 70 years inclusive, at screening
2. Confirmed clinical diagnosis of ED for more than 3 months according to the NIH Consensus Statement ('the inability to achieve or maintain penile erection sufficient for satisfactory sexual performance at least once')
3. Subject answers 'yes' to the question regarding the presence of residual EF over the past 3 months: *'At home over the past 3 months, have you experienced at least some growth of your penis in response to: (1) mechanical stimulation by yourself or your partner, or (2) visual stimulation?'*
4. Subject has been involved in a continuous heterosexual relationship for at least 6 months prior to screening
5. Documented written informed consent from both subject and his female partner
6. If the male subject's female partner is of childbearing potential from the time of first sexual intercourse attempt during the screening period until the last administration of study treatment, then the couple must have been using a medically acceptable form of contraception for at least 3 months prior to entering the study, and agree to continue such use for at least 1 month after the last study drug administration

Acceptable methods of contraception are listed below; it should be noted that condoms, femidoms, diaphragms, caps or hormone rings are not permitted as a form of contraception in this study:

- Surgical sterilisation of the male partner (vasectomy with documentation of azoospermia if possible)
- The female partner has undergone documented tubal ligation (female sterilisation)
- The female partner uses combined hormone injectables

- The female partner uses medically prescribed hormonal implants
- The female partner has undergone documented placement of an intrauterine device (IUD) or intrauterine system (IUS)
- The female partner uses combined oral contraceptives
- The female partner uses progesterone only contraceptives
- The female partner uses combined hormonal patches

Other than for male/female sterilisation, if any of these above listed methods are being used then their effectiveness must be determined by the PI or their delegate, taking into consideration the compliance and tolerance of the female partner with this method of contraception.

Subjects who are or wish to become pregnant will not be included in the study.

7. Subject and his female partner are capable of understanding and complying with the requirements of the protocol and must have signed the ICF prior to participation in any study-related procedures
8. Low IIEF-EF scores (≤ 25) during the screening period

To continue in the open-label extension phase of the study, subjects must meet the following inclusion criteria at the follow-up visit of the double-blind phase (Visit 6):

1. Subject and his female partner complete the double-blind phase
2. Subject and his female partner were compliant to study procedures during the double-blind phase
3. Documented written informed consent from both subject and his female partner
4. If the male subject's female partner is of childbearing potential from the time of first sexual intercourse attempt during the screening period until the last administration of study treatment, then the couple must have been using a medically acceptable form of contraception for at least 3 months prior to entering the study, and agree to continue such use for at least 1 month after the last study drug administration

Acceptable methods of contraception are listed below; it should be noted that condoms, femidoms, diaphragms, caps or hormone rings are not permitted as a form of contraception in this study:

- Surgical sterilisation of the male partner (vasectomy with documentation of azoospermia if possible)
- The female partner has undergone documented tubal ligation (female sterilisation)
- The female partner uses combined hormone injectables
- The female partner uses medically prescribed hormonal implants
- The female partner has undergone documented placement of an intrauterine device (IUD) or intrauterine system (IUS)
- The female partner uses combined oral contraceptives
- The female partner uses progesterone only contraceptives
- The female partner uses combined hormonal patches

Other than for male/female sterilisation, if any of these above listed methods are being used then their effectiveness must be determined by the PI or their delegate, taking into consideration the compliance and tolerance of the female partner with this method of contraception.

Subjects who are or wish to become pregnant will not be included in the study.

9.3 Exclusion Criteria

Subjects are prohibited from participating in the study if they meet any of the following exclusion criteria (following screening [Visit 1], an eligibility check will be carried out on Day 1 of the treatment period [Visit 2]):

1. Any significant or serious cardiovascular, pulmonary, hepatic, renal, gastrointestinal, haematological, endocrinological, metabolic, neurological or psychiatric disease which, in the opinion of the PI, renders the subject unfit to take part in the study
2. Subject has any history of an unstable medical or psychiatric condition or using any medication that, in the opinion of the PI, is likely to affect the subject's ability to complete the study or precludes the subject's participation in the study

Certain concomitant medications; e.g. other vasodilators, calcium channel blockers, angiotensin converting enzyme (ACE) inhibitors, beta blockers, diuretics, anti-hypertensives, tricyclic anti-depressants and major tranquillisers, as well as the consumption of alcohol, may potentiate the BP lowering effects of MED2005; therefore, the PI must consider this carefully and include subjects at their discretion

3. Any presence of a symptomatic, active urinary tract infection diagnosed by the PI or their delegate at screening or during the study
4. Any presence of chronic indwelling urethral catheterisation or penile anatomical abnormalities (e.g. penile fibrosis) that would significantly impair EF
5. Any history of operations for Peyronie's disease
6. Primary hypoactive sexual desire or any history of hypogonadism
7. Any history of radical prostatectomy
8. Any history of severe/uncontrolled diabetes
9. Subjects taking two or more anti-hypertensives for the treatment of BP
10. Hypersensitivity to GTN or to any of the excipients, or idiosyncratic reactions to other organic nitrates
11. Concomitant treatment with sildenafil citrate, tadalafil, vardenafil and other PDE-5 inhibitors
12. Subjects taking Alpha blockers
13. Subjects receiving testosterone pellets
14. Any penile surgery except circumcision
15. Any treatment with acetyl cysteine within 6 months
16. Any treatment with dihydroergotamine within 6 months
17. Postural hypotension, hypotension or uncorrected hypovolaemia, as the use of GTN in such states could produce severe hypotension or shock

18. Increased intracranial pressure (e.g. head trauma or cerebral haemorrhage) or inadequate cerebral circulation
19. Any history of migraine or recurrent headache
20. Aortic or mitral stenosis
21. Hypertrophic obstructive cardiomyopathy
22. Constrictive pericarditis or pericardial tamponade
23. Closed-angle glaucoma
24. Subjects with nursing partners, known pregnant partners or with partners who wish to become pregnant during the course of the study
25. Confirmed positive results from urine drug screen (amphetamines, benzodiazepines, cocaine, cannabinoids, opiates, barbiturates, tricyclic antidepressants and methadone) or from the alcohol breath test at screening (for clarification, **any** positive result from the urine drug screen or alcohol breath tests at screening will mean the subject will be excluded from the study). In the instance that a subject is using medication which may give a positive result, exclusion will be at the PI's discretion
26. Subject has recent (last 12 months) clinical evidence of alcoholism or drug abuse.
27. Subject has a positive screen for hepatitis B, consisting of hepatitis B surface antigen (HBsAG), hepatitis C antibody, and human immunodeficiency virus (HIV)
28. Any clinically significant abnormal laboratory, vital signs or other safety findings as determined by medical history, physical examination or other evaluations conducted at screening or on admission
29. Subjects unwilling to cease use of vacuum devices, intracavernosal injections, PDE-5s or other therapy for ED for the entire course of the study
30. Unwillingness of the subject or their partner to agree to make the required attempts at sexual intercourse during treatment period
31. Any history of unresponsiveness to PDE-5 treatment or significant side-effects, excluding visual disturbances, with PDE-5s
32. Fewer than four attempts at sexual intercourse during the screening period
33. Subjects or their partners who are illiterate or are unable to understand the language in which the questionnaires are available
34. Subject has received any investigational product during the 90 days prior to dosing for this study
35. Subject or his partner cannot communicate reliably with the PI
36. Subjects with severe premature ejaculation (little or no control of ejaculation at the time of penetration)

Subjects are prohibited from participating in the open-label extension phase of the study if they meet any of the following exclusion criteria at the follow-up visit of the double-blind phase (Visit 6):

1. Subsequent to recruitment into the double-blind phase of the study, the development of any significant or serious cardiovascular, pulmonary, hepatic, renal, gastrointestinal, haematological, endocrinological, metabolic, neurological or psychiatric disease which, in the opinion of the PI, renders the subject unfit to continue in the open-label extension phase of the study

2. Subject using any medication that, in the opinion of the PI, is likely to affect the subject's ability to complete or participate in the open-label phase of the study.

NB The concomitant medications listed as exclusion criteria for the study apply to the open-label extension phase. Certain concomitant medications; e.g. other vasodilators, calcium channel blockers, ACE inhibitors, beta blockers, diuretics, anti-hypertensives, tricyclic anti-depressants and major tranquillisers, as well as the consumption of alcohol, may potentiate the BP lowering effects of MED2005; therefore, the PI must consider this carefully and include subjects at their discretion

3. Any presence of a symptomatic, active urinary tract infection diagnosed by the PI or their delegate at the start of the open-label extension phase
4. Subsequent to recruitment into the double-blind phase of the study, the development of postural hypotension, hypotension or uncorrected hypovolaemia, increased intracranial pressure or inadequate cerebral circulation, any clinically significant vital signs or other safety findings as determined by medical history, physical examination or other evaluations conducted at Visit 6 prior to recruitment to the open-label phase

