6.3.3 Efficacy and Safety

The efficacy and safety of MED2005 was assessed in a recent Phase IIa, multi-centre, randomised, double-blind, placebo-controlled, crossover study in male subjects clinically diagnosed with ED (Study FM53). The application of 0.6 mg MED2005 gel to the glans penis was associated with a statistically significant increase (i.e. improvement) in the EF domain score of the International Index for Erectile Function (IIEF; the primary endpoint) compared with a placebo gel. The efficacy of MED2005 compared with placebo was further supported by the analyses of the secondary efficacy outcome variables.

The tolerability and safety profile of MED2005 appears to be predictable and consistent with the known pharmacological profile of GTN. In Study FM53, 15 mild related headaches were reported in 1023 intercourse attempts and only 2 mild related headaches were reported by the female partners.

The Phase I, healthy volunteer studies FM33, FM35 and FM58 demonstrated a favourable safety profile of MED2005. There was a low incidence of mild transient headache, no clinically significant effects on blood pressure (BP) and no serious adverse events (SAEs). In the Phase IIa study in male subjects clinically diagnosed with ED (FM53), a locally applied dose of MED2005 was considered safe, well-accepted and well-tolerated by the male subjects and their female partners. FMD has also conducted a single-blind, placebo-controlled, dose-ranging study to assess the physiological effects and tolerability of a different GTN gel formulation (Zanafil) applied to the vaginas of a group of healthy, pre-menopausal, female volunteers (Study FM22). No AEs were reported following vaginal application of 0.5 mg and 1 mg doses of GTN gel. This suggests that even if the full dose of MED2005 was transferred to the female partner during sexual intercourse, it would be unlikely to cause any notable tolerability problems.

For further safety information, please refer to the 'Reference Safety Information' of the current version of MED2005 IB.

Additional studies in subjects with ED are required to further demonstrate the efficacy and safety of MED2005. This is the reason for the current study.

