6.4.2 Potential Risks

Preclinical studies demonstrate that GTN does not possess teratogenic potential, has no adverse effects on male or female reproductive organs and is unlikely to have the potential to cause sensitisation or irritation at the intended site of application in men or women.

Published clinical studies and literature reports confirm the pharmacologically predictable tolerability profile of GTN. The most common AEs that have been reported are headache (generally mild and short-lived) and hypotension (not normally symptomatic). The literature reports relative success following the application of GTN transdermal patches or GTN ointment to the shaft of the penis.

GTN has been used in clinical practice in numerous countries for more than 100 years for the treatment of angina pectoris and other cardiovascular conditions. The side-effects of GTN are well documented and reports indicate that the most common undesirable effects include headache, facial flushing and nausea. In subjects treated with GTN ointments, for example for rectal pain or angina prophylaxis, the reported AEs are similar to those documented for other GTN treatments. For the treatment of rectal pain, the most commonly reported treatment-related AEs using Rectogesic® 4 mg/g rectal ointment were dose-dependent increases in headache (57% of subjects) followed by dizziness and nausea [19]. For prophylaxis of angina pectoris, AEs related to Percutol® 2% ointment have also been shown to be dose-related and almost all were the result of vasodilator activity. Headache was the most commonly reported AE [20]. Other commonly reported AEs with GTN 2% ointment include nausea and vomiting. Uncommon side-effects include cardiac disorders (tachycardia, bradycardia [in the presence of syncope]), vascular disorders (hypotension, circulatory collapse), allergic skin disorders (eczema, dermatitis, pruritus, urticaria, non-specific rashes) and immune system disorders (hypersensitivity reactions, anaphylaxis).

The study is designed for careful monitoring of any potential AEs of MED2005.

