11.1.2 Screening Assessments (Visit 1)

Visit 1 must be attended by the male subject and his female partner. Following written informed consent, the following assessments should be carried out during the screening period between Day -43 and Day -1:

- Eligibility check
- Medical history (including history of ED and surgical history)
- Full physical examination (including height, weight and body mass index [BMI])
- Alcohol breath test
- Urine drugs of abuse screen
- Vital signs (BP, HR and body temperature)
- Laboratory safety assessments (haematology, biochemistry and urinalysis)
- 12-lead ECG (in triplicate, approximately 1 minute apart)
- Serology
- Endocrinology
- Training in the use of subject questionnaires and IMP application
- AE review
- Prior and concomitant medications and procedures
- SEAR questionnaire (male subject and his female partner)
- PGI-S (male subject only)

During the screening period (between site Visits 1 and 2), subjects and their partners are required to make a minimum of four attempts at sexual intercourse (without treatment) within a 4-week period at their convenience. The following assessments should be carried out during this time:

- SEP questionnaire (to be completed by the subject and his partner at home after each sexual intercourse attempt)
- Pre-screening IIEF questionnaire (i.e. IIEF-EF Question 1 to 5 and 15 only) to be completed by the subject at the end of the screening period on site, to confirm eligibility.

Subjects who cannot comply with the minimum number of intercourse attempts or who exceed 25 on the IIEF-EF will be excluded from the study before randomisation and dosing.

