12.1 Adverse Events

12.1.1 Definitions

The definitions of AEs, adverse drug reactions (ADRs), SAEs and suspected unexpected serious adverse reactions (SUSARs) are given below. It is of the utmost importance that all staff involved in the conduct of clinical research are familiar with the contents of this section.

Adverse Event

An AE is any untoward medical occurrence (including the deterioration of a pre-existing medical condition) in a patient or clinical investigation subject administered a pharmaceutical product and which does not necessarily have to have a causal relationship with this treatment. An AE can therefore be any unfavourable and unintended sign (including an abnormal laboratory finding, for example), symptom or disease temporally associated with the use of a medicinal product, whether or not considered related to the medicinal product. In clinical studies, an AE can include an undesirable medical occurrence occurring at any time, from the date informed consent was signed until the end of their participation in a study; i.e. the subject has discontinued or completed the study.

The causality of AEs (i.e. their relationship to study treatment) will be assessed by the PI who, in completing the relevant eCRF, must answer 'yes' or 'no' to the question: 'Do you consider that there is a reasonable possibility that the event may have been caused by the study medication?'

The following factors should be considered when deciding if there is a 'reasonable possibility' that an AE may have been caused by the study medication (that is, there are facts/evidence or arguments to suggest a causal relationship):

- Time course and exposure to suspect drug: Has the subject or their female partner actually received the suspect drug? Does the AE have a reasonable temporal relationship to the administration of the suspect drug?
- Consistency with known drug profile: Is the AE consistent with previous knowledge of the suspect drug (pharmacology and toxicology) or drugs of the same pharmacological class? OR, could the AE be anticipated from its pharmacological properties?
- No alternative cause: The AE cannot be reasonably explained by another aetiology such as the underlying disease, other drugs, other host or environmental factors
- Laboratory tests: A specific laboratory investigation (if performed) has confirmed the relationship?

A 'reasonable possibility' could be considered to exist for an AE where one or more of these factors exist.

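### Exclusion criterion 10 does not name the female partner, so a couple in which she has a known hypersensitivity to GTN or an excipient is not clearly excluded

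*Protocol*

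**What the plan says.** Protocol section 9.3 lists 36 exclusion criteria for the double-blind phase, introduced as applying to subjects. Criterion 10 is "Hypersensitivity to GTN or to any of the excipients, or idiosyncratic reactions to other organic nitrates", with no statement of whose hypersensitivity is meant. Section 9.2, inclusion criterion 1, describes the subject as a man aged 18 to 70.

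On the partner's exposure:

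- Section 8.2.4 lets either member of the couple apply the gel.
- Section 9.4 rules out condoms and femidoms as contraception.
- Section 6.3.3 discusses tolerability "even if the full dose of MED2005 was transferred to the female partner during sexual intercourse".
- Section 9.6.1 speaks of withdrawing subjects and their partners from study drug.
- The causality factors in section 12.1.1 include the question "Has the subject or their female partner actually received the suspect drug".

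On the risk, section 6.4.2 first reports that preclinical work makes sensitisation or irritation at the application site unlikely in men or women. Later, after a sentence about a 2% GTN ointment, it lists uncommon side-effects that include "immune system disorders (hypersensitivity reactions, anaphylaxis". On experience in women, section 6.3.3 reports from a volunteer study of a different GTN gel that "No AEs were reported following vaginal application of 0.5 mg and 1 mg doses of GTN gel", and from the Phase IIa study (FM53, 0.6 mg) that "only 2 mild related headaches were reported by the female partners".

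On screening, section 11.1.2 says "Visit 1 must be attended by the male subject and his female partner".

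**The concern.** A hypersensitivity exclusion exists to keep people who are known to react away from the product. Here two people may come into contact with it, and the criterion most naturally reaches one of them. A site that applies the list as most readers would could enrol a couple in which the woman has a known reaction to GTN, to another organic nitrate or to an excipient, and she would then be exposed at home. About 50 sites in several countries will apply this line, so two plausible readings may well lead to different practice. At stake is an avoidable safety risk to a consenting participant. No estimand, power, type I error or analysis result depends on it.

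**Working it through.** There is no figure in the plan to reproduce. The check is a reading of the eligibility text against the exposure text, plus simple arithmetic on scope.

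**1. Whom does criterion 10 reach?** Four criteria in section 9.3 name the partner: 24 (nursing or pregnancy), 30 (unwillingness to make the attempts), 33 (literacy and language) and 35 (communication). That is 4 of 36. Criterion 10 is not among them. Several nearby criteria that also name no person (Peyronie's operations, radical prostatectomy, penile surgery) can only concern the man. Section 9.4, by contrast, opens by addressing subjects and their female partners together, so the drafters did name her when they meant her. The man-only reading is the more natural one.

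**2. Is that reading forced?** No. Section 9.2 states "Subjects who are or wish to become pregnant will not be included in the study", where the word for participant can only mean the woman, and footnote g to Table 1 refers to female subjects. An investigator who applied criterion 10 to both partners would contradict nothing. The scope is therefore ambiguous.

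**3. Does another criterion or screening step cover her?** Criteria 1 and 2 refer to the subject, and criterion 28 falls under the same introduction. The Visit 1 list in section 11.1.2 marks some items for both partners and one for the man only, but nothing states that a medical history is taken from the woman. Section 11.4.3 does not say so either. In Table 1, informed consent is marked for male and female, and medical history is not. No listed question asks her about hypersensitivity.

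**4. Do the tolerability data answer the point?** The volunteer study used 0.5 mg and 1 mg of another gel in healthy women; two of the three doses here, 1.2 mg and 1.8 mg, are higher. FM53 used 0.6 mg. These data are reassuring for women in general. They do not address a woman already known to react.

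**5. Scope of the wording.**

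- Planned partners: 1000, one per subject.
- In couples allocated to a GTN gel under 1:1:1:1: 3/4 × 1000 = 750.
- In couples allocated to vehicle: 1/4 × 1000 = 250. Only the excipient part of the criterion matters for them.
- Treated attempts requested per couple: at least 4 per period × 3 periods = 12.

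These numbers say how many people the sentence might apply to. They do not measure risk. The relevant quantity is the number of partners with a known hypersensitivity. The protocol does not give it, and it is expected to be very small, so no count of affected couples is computed.

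**The case against.** The strongest reply has four parts.

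**Ambiguity.** Loose use of the word for participant allows a site to read criterion 10 as covering both partners. This stands, and it rules out the stronger inference that the protocol positively admits hypersensitive partners. It does not make the criterion clear.

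**Risk context.** A reader might infer from section 6.4.2 that anaphylaxis is an established hazard of this gel for partners. The text does not support that. The same section considers sensitisation at the application site unlikely in men or women, and the list containing anaphylaxis follows a sentence on a 2% ointment. The trial gels are 0.2% to 0.6%, so the ointment is 2/0.6 = 3.3 to 2/0.2 = 10 times as concentrated. This lowers the concern but does not remove it: being unlikely to cause sensitisation says little about a woman who is already hypersensitive, and criterion 10 excludes hypersensitive men from these same strengths. The discussion of whole-dose transfer is likewise a worst case used to argue tolerability, not a prediction.

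**Existing protection.** A reader might infer that she is unprotected. She is not. She consents in her own right after written information and an explanation that may include risks (section 16.3.1), attends Visits 1 and 2, is trained in application, keeps a real-time adverse event diary and may be withdrawn from study drug at any time. For harm to occur, a woman who knows she reacts would have to consent and be accepted by the investigator. The consent pages and the Investigator's Brochure are not available here, so a warning in either cannot be ruled out. A warning would still not be an exclusion criterion, and the diary and withdrawal rules act only after exposure.

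**No statistical consequence.** This is correct, and none is claimed.

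**Conclusion.** The point holds as a minor safety clarification. Criterion 10 most naturally covers only the man, the protocol treats the woman as potentially exposed, and no other stated criterion or screening question clearly covers her known hypersensitivity. The conclusion rests on the eligibility text and listed screening procedures as written, and on the judgement that a criterion naming no person, under an introduction addressed to subjects, will usually be applied to the male subject. The expected number of affected couples is very small and cannot be estimated from the document. It would go too far to conclude that the criterion is plainly wrong, that women known to react will in fact be enrolled, or that any efficacy or safety analysis is compromised.

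**What to change.** Begin criterion 10 with *Subject or his female partner has known*, and leave the rest of its wording, including the excipients and the other organic nitrates, unchanged. Add one matching question to the partner at Visit 1. No extra visit or test is needed, and the downside is a very small number of additional screen failures.

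No separate change to the extension-phase criteria is proposed. Entry there already requires that both partners completed the double-blind phase, complied with procedures and gave renewed consent, and adverse event review and the withdrawal rules largely cover a partner who reacted.
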